2.3.2 DLT-evaluable population

The DLT evaluable population is defined as patients in the Phase 1 part receiving the planned doses of isatuximab and REGN2810 during Cycle 1, and who completed the DLT observation period after the first IMP administration as per Section 9.1.1 from protocol, unless they discontinue the study treatment(s) due to DLT. The dose recommended for Phase 2 will be determined on the DLT evaluable population.

2.3.3 Pharmacokinetic population

The PK population will be defined independently for isatuximab and REGN2810, and include patients from the all treated population with at least one reportable concentration after the study drug administration (whatever the cycle and even if dosing is incomplete).

2.3.4 Pharmacodynamic population

The pharmacodynamic population will include patients from the all-treated population with at least 1 pharmacodynamic marker result after the first dose of study treatment.

2.3.5 Anti-drug antibody (ADA) evaluable population

The ADA evaluable population will be defined independently for isatuximab and REGN2810, and include subjects with at least one sample, taken post-baseline after drug administration during the

treatment or follow-up observation period, that is appropriate for ADA testing with a reportable result (positive, negative or inconclusive).

2.3.6 Cross-over population

The cross-over population is defined as patients in Cohort A-2 who progressed on isatuximab monotherapy and received isatuximab in combination with REGN2810.

2.3.7 Response evaluable population

The response evaluable population will include all patients in the all-treated population who fulfilled all inclusion and exclusion criteria with an evaluable baseline assessment and at least one evaluable post-baseline disease assessment during the treatment period.

2.4 STATISTICAL METHODS

Continuous data will be summarized using number of available data, mean, standard deviation, median, minimum and maximum for each dose level (if applicable). Categorical and ordinal data will be summarized using number and percentage of patients.

Data listings will be provided separately by cohort and sorted by patient number, unless otherwise specified.

2.4.1 Demographics and baseline characteristics

Demographics and baseline characteristics will be summarized on the all-treated population. Parameters described in [Section 2.1.1](#) will be summarized using descriptive statistics.

The medical and surgical history will be summarized according to the SOC and PT (SOC will be sorted according to the internationally agreed order and PT by overall decreasing frequency).

Disease characteristics at diagnosis and at study entry will be described.

2.4.2 Prior or concomitant medications (other than anticancer therapies)

The prior, concomitant and post medications will be presented for the all-treated population. The anti-cancer therapy will be presented separately.

Medications will be summarized according to the WHO-DD dictionary, considering the first digit of the anatomic therapeutic category (ATC) class and the first 3 digits of the ATC class (therapeutic category). All ATC codes corresponding to a medication will be summarized, and the patients will be counted once in each ATC category (anatomic or therapeutic) linked to the medication. Therefore the patients may be counted several times for the same medication.

The tables for medications (prior, concomitant and post-treatment) will be sorted by decreasing frequency of ATC followed by all other therapeutic classes based on the overall incidence. In case of equal frequency regarding ATCs, alphabetical order will be used.

IAR medications

Number (%) of patients with IAR medications as defined in [Section 2.1.2](#) will be provided.

2.4.3 Anticancer therapies

Prior anti-cancer treatments will be summarized for the all-treated population. Number (%) of patients with the anti-cancer treatments described in [Section 2.1.1](#) will be summarized. In addition, prior anti-cancer treatments after disease became mCRPC for prostate patients or after disease became advanced for NSCLC patients will be summarized.

2.4.4 Extent of investigational medicinal product exposure and compliance

The extent of study treatment exposure will be assessed and summarized on the all-treated population.

2.4.4.1 Extent of investigational medicinal product exposure

The overall extent of exposure will be assessed as:

- Overall number of cycles started
- Duration of overall exposure (weeks): defined as (last day of last cycle – first day of first cycle)/7. The first day of first cycle is defined as the date of the first dose of study treatments. The last day of last cycle is defined as the later date among the following:
 - Date of the last dose of isatuximab + 7 days if the last cycle is a QW cycle or date of the last dose of isatuximab + 21 days if the last cycle is a Q3W
 - Date of the last dose of REGN2810 + 21 days

Total number of cycles started, number of cycles started by patient as a continuous variable and by category (ie, number [%] of patients receiving at least 1 cycle, at least 2 cycles, etc.), duration of overall exposure will be summarized using descriptive statistics.

To describe overall dose modification, the cycle delay will be summarized. A cycle is considered as delayed if the start date of cycle – 21 – the start date of the previous cycle is >3 days. They cycle start date is defined as the earlier date of isatuximab or REGN2810 administration within a cycle. Cycle delay is not defined for the first cycle.

Cycle delay will be summarized at both the patient and cycle levels as follows:

- Patient level:
 - Number of patients treated
 - Number (%) of treated patients with at least 1 cycle delayed
 - Number (%) of treated patients with a cycle delayed between 4 and 7 days
 - Number (%) of treated patients with a cycle delayed between 8 and 14 days
 - Number (%) of treated patients with a cycle delayed more than 14 days

- Cycle level:
 - Number of cycles started
 - Number (%) of cycles delayed
 - Number (%) of cycles delayed between 4 and 7 days
 - Number (%) of cycles delayed between 8 and 14 days
 - Number (%) of cycles delayed more than 14 days

2.4.4.2 Isatuximab exposure

The isatuximab exposure will be summarized as follows:

- Total number of cycles started
- Number of cycles started by patient as a continuous variable and by category
- Duration of isatuximab exposure (weeks) is defined as
 - (Date of the last dose of isatuximab + 7 days – date of the first dose of isatuximab)/7 if the last cycle is a QW cycle
 - (Date of the last dose of isatuximab + 21 days – date of the first dose of isatuximab)/7 if the last cycle is a Q3W cycle
- Actual dose (mg/kg): is defined as the actual dose (mg) administered divided by the body weight at the time
- Cumulative dose (mg/kg): the cumulative dose is the sum of all actual doses (mg/kg) of isatuximab given from the first to the last administration
- Actual dose intensity (ADI, mg/kg/week): is defined as the cumulative dose (mg/kg) divided by the duration of isatuximab exposure (weeks)
- Relative dose intensity (RDI, %): $100 \times \frac{\text{ADI (mg/kg/week)}}{\text{Planned Dose Intensity (mg/kg/week)}}.$

Planned dose intensity (mg/kg/week) corresponds to the planned dose (mg/kg) multiplied by the theoretical total number of doses during the started cycles (3 for QW cycle and 1 for Q3W cycle) and divided by the theoretical cycle duration (weeks), ie, 3 weeks per cycle started.

The total number of cycles started, number of cycles started by patients as a continuous variable and by category (ie., number [%] of patients receiving at least 1 cycle, at least 2 cycles, etc.), duration of isatuximab exposure, cumulative dose, ADI and RDI will be summarized by descriptive statistics.

The following variables will be derived to describe dose delay and modification:

- Dose delay within Cycle 1: a dose is deemed as delayed within Cycle 1 if the actual start date of the infusion is ≥ 2 days beyond the theoretical day of treatment for weekly dose.
Dose delay does not apply to the first infusion of Cycle 1

- Infusion interruption: an infusion is considered to be interrupted (as collected on eCRF) if the isatuximab administration is stopped during an infusion before it is completed regardless of whether it is further restarted or not
- Dose omission: a dose is considered omitted if the dose is not administered for the scheduled visit and there are dose(s) administered afterwards

Dose delay and modification will be summarized at the patient and infusion levels as follows:

- Patient level:
 - Number (%) of patients with at least 1 dose delay within cycle
 - Number (%) of patients with at least 1 dose omission
 - Number (%) of patients with at least 1 infusion interrupted
 - Number (%) of patients with at least 1 infusion interrupted and re-started
 - Number (%) of patients with at least 1 infusion interrupted and not re-started
- Infusion level:
 - Number of isatuximab infusions
 - Number (%) of infusions interrupted
 - Number (%) of infusions interrupted and re-started
 - Number (%) of infusions interrupted and not re-started
 - Number (%) of infusions interrupted more than once
 - Number (%) of infusions interrupted at 1st infusion, 2nd infusion, subsequent infusions
 - Time from infusion start to first interruption in minutes summarized as a continuous variable and by category (<5 minutes, 5-10 minutes, etc.)

2.4.4.3 REGN2810 exposure

The REGN2810 exposure will be summarized as follows:

- Total number of cycles started
- Number of cycles started by patient as a continuous variable and by category
- Duration of REGN2810 exposure (weeks) is defined as (Date of the last dose of REGN2810 + 21 days – Date of the first dose of REGN2810)/7
- Actual dose (mg): is defined as actual dose administered
- Cumulative dose (mg): the cumulative dose is the sum of all actual REGN2810 doses
- ADI (mg/week): is defined the cumulative dose (mg) divided by the duration of REGN2810 exposure (weeks)
- RDI (%): $100 \times \frac{\text{ADI (mg/week)}}{\text{Planned Dose Intensity (mg/week)}}$, where the planned dose intensity (mg/week) is 116.7 mg/week for Q3W schedule

The total number of cycles started, number of cycles started by patients as a continuous variable and by category (ie, number [%] of patients receiving at least 1 cycle, at least 2 cycles, etc), duration of REGN2810 exposure, cumulative dose, ADI and RDI will be summarized by descriptive statistics.

The following variables will be derived to describe dose delay and modification:

- Infusion interruption: An infusion will be considered to be interrupted (as collected on eCRF) if the REGN2810 administration is stopped during an infusion before it is completed regardless of whether it is further restarted or not
- Dose omission: a dose is considered omitted if the dose is not administered for the scheduled visit and there are positive dose(s) afterwards

Dose delay and modification will be summarized at the patient and infusion levels as follows:

- Patient level:
 - Number (%) of patients with at least 1 dose omission
 - Number (%) of patients with at least 1 infusion interrupted
 - Number (%) of patients with at least 1 infusion interrupted and re-started
 - Number (%) of patients with at least 1 infusion interrupted and not re-started
- Infusion level:
 - Number of REGN2810 infusions
 - Number (%) of infusions interrupted
 - Number (%) of infusions interrupted and re-started
 - Number (%) of infusions interrupted and not re-started
 - Number (%) of infusions interrupted more than once
 - Number (%) of infusions interrupted at 1st infusion, 2nd infusion, subsequent infusions
 - Time from infusion start to first interruption in minutes summarized as a continuous variable and by category (<5 minutes, 5-10 minutes, etc.)

2.4.5 Analyses of efficacy endpoints

All efficacy analysis will be performed using the all-treated population. In addition, efficacy analysis will be performed using the response evaluable population.

For each cohort, the analysis cut-off date for the primary analysis of RR will be 6 months after the last patient's first treatment in the cohort. The analysis cut-off date for secondary efficacy endpoints including DoR and PFS will be 12 months after the last patient's first treatment in the cohort. The primary analysis of RR will be updated.

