- x Immunophenotyping: a sample of peripheral blood will be drawn at Cycle 1 Day 1, Cycle 2 Day 1 and Cycle 3 Day 1 and then on Day 1 prior to IMP administration of each odd cycle starting from Cycle 5 (eg Cycle 5, Cycle 7, Cycle 9, Cycle 11, etc), at the EOT visit, and at follow-up (60 days after last IMP administration).
- y Plasma or serum cytokine concentration: A sample of peripheral blood will be drawn at baseline and Cycle 1 Day 1, Cycle 2 Day 1, Cycle 3 Day 1 and then on Day 1 prior to IMP administration at each odd cycle starting from Cycle 5 (ie, Cycle 5, Cycle 7, Cycle 9, Cycle 11 etc), at the EOT visit and at follow-up (60 days after last IMP administration).
- z Tumor assessment: CT or MRI of the chest, abdomen, pelvis and any other locations with suspicion or evidence of disease involvement is to be performed in all patients at screening (diagnostic quality scans performed as part of routine clinical management within 28 days prior to IMP initiation are acceptable). Repeat every 9 weeks starting at the end of Cycle 3 (63 ±7 days; disease assessment timing should follow calendar days and should not be adjusted for delays in cycle start), whenever disease progression is suspected, at the EOT visit (if not performed in the past 30 days) and during follow-up (if discontinue IMP without PD, repeat every 90 days), using the same method for each assessment. If tumor assessment status is partial or complete response, changes in tumor measurements must be confirmed by repeat assessments that should be performed no less than 4 weeks after the criteria for response are first met. Initial evidence of progression should be confirmed no less than 4 weeks later, see Section 6.7.1. Tumor assessment is not needed for patients who start another anti-cancer treatment regimen. Study sites must retain disease assessment images, as Sponsor may decide to collect these images for possible Independent Central Review in the future.

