- aa PSA assessment: For patients with mCRPC, to be performed at baseline (within 14 days before initiation of IMP). Repeat at Cycle 1 Day 1, every 9 weeks starting at the end of Cycle 3 (63 ±7 days; disease assessment timing should follow calendar days and should not be adjusted for delays in cycle start), at the EOT visit (if not performed in the past 30 days) and during follow-up (if discontinue IMP without PD, repeat every 90 days). PSA responses are to be confirmed no less than 4 weeks later. PSA assessment is not needed for patients who start another anti-cancer treatment regimen.
- bb Bone scan: Mandatory for patients with mCRPC (diagnostic quality scans performed as part of routine clinical management within 6 weeks prior to IMP initiation are acceptable). Repeat every 9 weeks at the end of Cycle 3 (63 ±7 days; disease assessment timing should follow calendar days and should not be adjusted for delays in cycle start), at the EOT visit (if not performed in the past 30 days) and during follow-up (if discontinue IMP without PD, repeat every 90 days). If progression is defined by bone scan only, the bone scan should be repeated no less than 6 weeks to confirm the progression, see Section 6.7.1. In case of doubtful lesions on bone scan, bone-centered X-ray or MRI scan should be performed to confirm the nature of those lesions (metastatic or not). Study sites must retain disease assessment images, as Sponsor may decide to collect these images for possible Independent Central Review in the future.
- cc REGN2810/Isatuximab Administration: At the start of each treatment cycle, the patient's weight will be determined. REGN2810 administration is only applicable in cohorts receiving isatuximab in combination with REGN2810.

Amended Clinical Trial Protocol No. 05 SAR650984-ACT15319 - isatuximab 11-Jun-2019 Version number: 1

dd AE/SAE assessment: All AEs, including adverse events of new onset as well as worsening of baseline signs and symptoms are to be reported from the signing of the informed consent to 30 days following the last administration of study treatment. After the 30 day all ongoing related non-serious AEs, ongoing SAE and new related AE/SAEs are to be followed to resolution or stabilization. Stabilization is defined as an AE ongoing without any change for at least 3 months. Severity will be graded according to NCI-CTCAE version 4.03.

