## 13.3.7 Response evaluable population

The response evaluable population will include all patients in the all-treated population who fulfill all eligibility criteria with an evaluable baseline assessment and at least one evaluable post-baseline response assessment during the treatment period.

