## 13.4.4.1 Analysis of primary efficacy endpoint

The RR will be summarized using descriptive statistics. A 90% 2-sided confidence interval will be computed using Clopper-Pearson method. The statistical inference will be based on the hypothesis defined in Section 13.1 using a 1-sided exact binomial test with a significance level of 0.05 for each cohort. For each cohort, the analysis cut-off date for the primary analysis of RR will be 6 months after the last patient's first treatment in the cohort. The analysis cut-off date for secondary efficacy endpoints including DoR and PFS will be 12 months after the last participant's first treatment in the cohort. The primary analysis of RR will be updated.

Same analysis will be performed for RR using the response evaluable population as a secondary analysis. Subgroup analyses for primary endpoint may be performed if relevant.

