2.3 ANALYSIS POPULATIONS

2.3.1 All-treated population

For both Phase 1 and Phase 2 parts of the study, the all-treated population will include all patients who signed the study informed consent and received at least 1 dose (even incomplete) of the study treatments, either isatuximab or REGN2810.

This population is the primary population for the analyses of efficacy and safety parameters except for DLT evaluation. All analyses using this population will be based on the dose level actually received in the first cycle.

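### SAP 2.4.5 extends the response evaluable population from RR to efficacy in general, which biases the supplementary OS, PFS/rPFS and DCR results upward

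*SAP*

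**What the plan says.** - **SAP 2.4.5** runs all efficacy analysis on the all-treated population and then adds: "In addition, efficacy analysis will be performed using the response evaluable population". It names no endpoints. The analyses placed under that heading, in 2.4.5.2, include PFS with a 6-month estimate, OS, rPFS, time to response and DCR ≥6 months.
- **Protocol 13.4.4.1** is narrower: "Same analysis will be performed for RR using the response evaluable population as a secondary analysis". Protocol 13.4.4.2, on secondary efficacy endpoints, does not mention this population.
- **SAP 1.5** gives modifications to the protocol's statistical section as not applicable.
- **Membership** requires full eligibility, an evaluable baseline and "at least one evaluable post-baseline disease assessment during the treatment period" (SAP 2.3.7). Protocol 13.3.7 has "at least one evaluable post-baseline response assessment during the treatment period".
- **Assessment timing** is in the Protocol 1.3 flowchart footnotes. For CT/MRI: "Repeat every 9 weeks starting at the end of Cycle 3 (63 ±7 days", and also "whenever disease progression is suspected, at the EOT visit (if not performed in the past 30 days". For PSA: "Repeat at Cycle 1 Day 1, every 9 weeks starting at the end of Cycle 3".
- **Status of all-treated**, SAP 2.3.1: "This population is the primary population for the analyses of efficacy and safety parameters except for DLT evaluation".

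**The concern.** Whether a patient belongs to the response evaluable population is settled by something that happens after first dose. OS, PFS and rPFS are timed from first dose (SAP 2.1.3.2 and 2.1.3.3), and DCR is divided by the size of the analysis population. A patient who fails before any evaluable assessment is therefore removed because of that failure, and the estimate rises.

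At stake is a set of supplementary tables and curves that would sit beside the all-treated results and look better than them for a reason unrelated to the drug. The protocol did not plan them, and the SAP does not declare them as an addition.

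**Working it through.** **1. Who is lost.** Patients with no evaluable post-baseline assessment, by what happens to them:

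| Patient | All-treated | Response evaluable |
|---|---|---|
| Dies unassessed | OS, PFS and rPFS event; DCR failure | absent |
| mCRPC, unequivocal clinical progression, unassessed | PFS event; DCR failure | absent |
| NSCLC, clinical deterioration only, unassessed, no PFS event | PFS censored on Day 1; DCR failure | absent |

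In the third row, Day 1 censoring (SAP 2.1.3.2) means that removal leaves the PFS curve unchanged; only DCR moves. A patient imaged early for suspected progression and found to have PD is in both populations.

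**2. Figures in the plan.** The documents give no expected share outside this population. The figures that can be reproduced are the Simon designs in protocol Table 8. By exact two-stage binomial, mCRPC (23/49, ≥3 then ≥9) gives alpha 0.0479 and power 0.9015. NSCLC (20/36, ≥2 then ≥5) gives alpha 0.0294 and power 0.9018. Both meet the stated 5% and 90%. They concern RR, whose primary population is all-treated, so this point does not touch them.

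**3. Size for OS.** Inputs: first scheduled assessment at day 63, or 63/30.4375 = 2.07 months (protocol 1.3); mCRPC median OS of 12.2 to 34.7 months (protocol 4.1.3.2). Assumptions: exponential survival, and no one who dies before day 63 has an evaluable assessment. The second makes d an upper bound.

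- Share excluded: d = 1 − 2^(−2.07/median)
- Survival at a later time t: S(t)/(1 − d)
- Median: median × [1 + log2(1/(1 − d))]

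| Median OS, all-treated | d | Median, response evaluable | 12-month OS, all-treated | 12-month OS, response evaluable |
|---|---|---|---|---|
| 12.2 months | 11.1% (5.4 of 49) | 14.3 months | 50.6% | 0.506/0.889 = 56.9% |
| 34.7 months | 4.1% (2.0 of 49) | 36.8 months | 78.7% | 0.787/0.959 = 82.0% |

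If half of the early deaths at the 12.2-month median did have an assessment, d = 5.5%, the median reads 13.2 months and 12-month OS 53.5%. The ±7-day window changes d at that median little: day 56 gives 9.9% and day 70 gives 12.2%.

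**4. Size for DCR and PFS.** The all-treated values here are assumed.

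- DCR 40%: 0.40/0.95 = 42.1% at d = 5%; 0.40/0.90 = 44.4% at d = 10%.
- 6-month PFS 30%: 0.30/0.95 = 31.6% and 0.30/0.90 = 33.3%, if every excluded patient is a PFS event before 6 months.

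The documents give no median OS for the NSCLC population, so I put no figure on that cohort.

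**The case against.** Several points on the other side stand and limit the finding.

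- **A scan is not required.** The texts say disease or response assessment, and for mCRPC a PSA value might be enough. It would not bring patients in on an earlier schedule, though: after Cycle 1 Day 1, scheduled PSA also starts at day 63 ±7.
- **Early deterioration does not by itself exclude a patient.** A reader might infer that everyone who worsens before week 9 is dropped, or that the curves begin with guaranteed event-free time. Imaging for suspected progression brings such patients in, and that scan can itself be the PFS event. End-of-treatment assessments may also bring patients in. Whether they fall within the treatment period is undefined for this population, and protocol 6.7.1 places them in safety follow-up.
- **Application to every endpoint is an inference.** The all-treated sentence in SAP 2.4.5 begins with the word all; the response evaluable sentence does not. SAP 2.4.5.2 has no analysis line for plain DCR, only for DCR ≥6 months. DOR is defined for responders only, so dropping unassessed patients does not affect it.
- **Nothing is decided on these results.** The study is non-comparative, and no decision rule uses them. Protocol 13.4.4 leaves further efficacy detail to the SAP, so the silence in SAP 1.5 is a weaker fault than a changed primary analysis would be.

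None of this removes the selection. With no endpoint limit, the SAP as written supports producing OS and PFS on a set of patients chosen by what happened after first dose.

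**Conclusion.** The point holds for the supplementary analyses. The SAP goes beyond the protocol's RR-only use without declaring it, and the assessment requirement pushes OS, PFS/rPFS and DCR (including DCR ≥6 months) upward. The eligibility and evaluable-baseline requirements also remove patients, in a direction that cannot be known in advance.

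The size rests on assumption. For OS in mCRPC, at most about 4% to 11% are excluded through early death. At a 12.2-month median this moves median OS to at most about 14.3 months and 12-month OS from 50.6% to 56.9%. This assumes exponential survival and no assessment in anyone who dies before day 63.

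A reader might go further in three ways that the documents do not support:

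- **That the trial's conclusions are biased.** All-treated is the primary population, and the Simon decisions are unaffected.
- **That a fifth of patients could be lost, lifting a 6-month OS of 75% to 0.75/0.80 = 94%.** Under constant hazard, 75% at 6 months implies 1 − 0.75^(2.07/6) = 9.4% dead by day 63. Eligibility also excludes ECOG ≥2 and predicted life expectancy under 3 months.
- **That RR on this population is a SAP error.** It is the protocol's own secondary analysis.

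**What to change.** In SAP 2.4.5, replace the open sentence with one limiting the response evaluable population to RR (with BOR) as a secondary analysis, as in protocol 13.4.4.1. State that PFS, rPFS, OS, DCR, DCR ≥6 months and the other time-to-event endpoints timed from first dose are analysed on the all-treated population only. Add a row, by cohort, giving the number of treated patients outside the response evaluable population and the reasons.

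Leave the definition in SAP 2.3.7 in line with protocol 13.3.7. Rewriting it to keep unassessed early failures as non-responders would depart from the protocol's definition and is not needed once the endpoints are limited.

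The cost is a wording change and fewer supplementary tables. No sample size, decision rule or primary result changes.
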